2.12.8 Specimen collection and management

Specimen Collection / Documentation:

Oral washes: Washes will be collected as described, de-identified and frozen for future microbiome studies.

Sputum Collection and Handling: Sputum will be collected by spontaneous expectoration if possible, or induction with hypertonic saline if needed as described above. After de-identification, sputum samples will be divided for nitrite measurements, microbiome studies, and quantitative CFU measurements. Sputum for nitrite measurements and microbiome studies will be immediately frozen. Sputum for CFU measurements will be packaged for shipping to the CF Foundation Microbiology Core Laboratory at University of Washington.

Blood Collection and Handling: Venous blood for screening labs and methemoglobin levels will be drawn by trained personnel. Samples will be sent to the hospital laboratory for analysis. Remaining sample will be bar coded and stored.

Specimen Handling and Labeling (De-Identification)

Specimens collected will be properly labeled. All research biological specimens and all records associated with the samples will be labeled only with a unique code that contains no personal identifiers. The information linking these code numbers to the corresponding subject's identity will be kept in a secure location in the investigator's office, and will not be available to staff managing samples at the research laboratories.

Immediately upon receipt of the biological specimens, all attempts will be made to process, isolate, collect, and store the specimens. The code number and date on which the specimen is frozen, all other information about the specimen, and subsequent processing will be entered on the specimen processing worksheet.

Specimen Management and Storage

Specimens in excess of immediate assay requirements may be stored indefinitely in a locked freezer under the control of the principal investigator.

The blood, sputum and oral wash samples will be stored after appropriate coding to remove patient identifiers. The coding information linking patient identifiers to the stored samples will be maintained in a locked, secure area that will be accessible only to the study investigator. Subjects may request to have their samples destroyed at any time. These samples will be destroyed immediately upon receipt of the subjects' written request to do so. Identification of which samples to destroy will be available from the coding information linking patient identifiers to the stored samples as described earlier in this paragraph.

Restrictions to Direct Access of Specimens

Specimens will be kept in the responsible study investigators' laboratories indefinitely and will be under the control of the principal investigator. Investigators or other personnel not involved with the management or operations of the study are not permitted direct access to the specimens.

2.13 ENDPOINTS

2.13.1 Primary endpoint: The primary endpoint is FEV₁ to assess for bronchoconstriction induced by the study compound. We will compare FEV₁ before and at 30, and 120 minutes after dosing on day 0 with 45 mg dose, and day 7 with 90 mg dose. A sustained decrease in FEV₁ > 15% with the 45 mg dose will be considered intolerance and the study subject will be removed from the protocol. If a subject tolerates one week of the 45 mg dose but has a sustained decrease in FEV₁ after getting the first 90 mg dose, the subject will remain on the 45 mg dose for the duration of the study. If a subject experiences a CF respiratory exacerbation as defined by a drop in FEV₁ >15% on the first set of spirometry at any visit compared with baseline spirometry, then the subject will be removed from the study.

2.13.2 Secondary endpoints:

- FE_{NO} (exhaled NO)
- sputum nitrite concentrations
- CF Questionnaire-R subsection
- quantitative bacterial cultures for *P. aeruginosa* and/or *S. aureus*
- methemoglobin levels measured both non invasively and in whole blood
- systolic blood pressure

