Experimental Procedure (visit 2/day 7 (+/- 1day)): This visit will take approximately 5-7 hours. Subjects will arrive and complete the CFQ-R CF Questionnaire. FENO will be measured as above. If the subject had no serious adverse events for the first seven days of the 45 mg dose of nebulized sodium nitrite, and has stable systemic blood pressure and FEV₁ on presentation to the Day 7 visit, an electronic nebulizer will be used to deliver 90 mg of nebulized sodium nitrite. Subjects will be monitored closely for the next two hours, including percutaneous measurements of oxygen saturation and methemoglobin levels, recorded at minutes 15, 30, 60 and 120, and noninvasive systemic blood pressure measurements every 15 minutes. If percutaneous methemoglobin measurements exceed 5%, they will be confirmed by venous blood measurement. Spirometry will be repeated at 30 and 120 minutes following nebulized sodium nitrite administration. If nebulized sodium nitrite is tolerated, then the subject will be dispensed an 8 day supply of 90 mg nebulized sodium nitrite dosed two times daily and discharged from the CTRC, CHP or the Emphysema Research Center in Montefiore. If the 90 mg dose of nebulized sodium nitrite was not tolerated, the subject will be observed. If FEV₁ returns to baseline in 4 hours and subject's SaO₂ is not greater than 5% drop from baseline and systolic BP is not greater than 40 mm Hg drop from pre-dose baseline, the subject will be re-challenged at this visit with a 45 mg dose of nebulized sodium nitrite and the observation protocol of blood pressure measurements, spirometry and percutaneous oxygen saturation measurement will be repeated.

Experimental Procedures (visit 3/day 14(+/- 1day)): This is a safety and tolerability visit and will take approximately 1 hour. Subjects will complete the CFQ-R and spirometry. An oral wash will be collected, and then a sputum sample will be collected. If the subject cannot spontaneously expectorate, then sputum induction will be done. The subject will then be discharged with a 15 day supply of nebulized sodium nitrite.

Experimental Procedures (visit 4/day 28(+/- 1day)): This visit will take approximately 1.5 hours. Subjects will complete the CFQ-R and spirometry. Expectorated or induced sputum will be collected, an oral wash will be collected, and FE_{NO} measured as above. Sputum will be used to measure nitrite concentration and quantitative bacterial load.

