2.6 STOPPING RULES

Two distinct scenarios in which subjects must be removed from the study are anticipated.

First, the subject experiences a CF respiratory exacerbation marked by a persistent drop in FEV1 >15% that is not temporally associated with nebulized sodium nitrite administration. The drop in FEV1 would be seen on the first set of spirometry at a visit, prior to dosing of nebulized sodium nitrite for that day. In this case, subjects will be removed from the study and referred to their pulmonologist for treatment of the CF respiratory exacerbation.

Drop in FEV1 >15% on the first set of spirometry, prior to drug administration, on any study visit when compared with baseline spirometry collected at screening.

In the second scenario, nebulized sodium nitrite is associated with a dose-dependent intolerance that will be seen at the dose escalation visit 2, or after receiving the first dose of drug on visit 1. Specific intolerances of concern are acute bronchospasm, hypotension or methemoglobinemia. In this case, if any one of the below occurs at the 45 mg dose, subject will be removed from the study; if any occur at the 90 mg dose, the subject will return to the previously tolerated dose of 45 mg.

Specific criteria for dose-dependent intolerance are:

Decrease in FEV1 by >15% between measurements on an individual study visit.

A decrease in systolic BP > 40 mmHg drop from pre-dose baseline or to <80mmHg and symptomatic.

SaO₂ drop below 88% and symptomatic or SaO₂ desaturation > 5% from baseline and symptomatic

A single occurrence of venous methemoglobin level >5%

Any serious adverse event thought to be possibly related to the study treatment

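### Section 2.13.1 drops the timing conditions from the exacerbation removal rule, and at Day 14 no visible text holds or times the morning home dose

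*Combined protocol and SAP*

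**What the plan says.** The exacerbation removal rule appears in three places in the combined protocol and SAP.

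- **2.13.1 (primary endpoint):** an FEV1 fall above 15% "on the first set of spirometry at any visit compared with baseline spirometry, then the subject will be removed from the study". No other condition is attached.
- **2.6 (stopping rules):** the fall must be persistent, must not be linked in time to nitrite, and must be seen "prior to dosing of nebulized sodium nitrite for that day". The bulleted criterion repeats the timing: "on the first set of spirometry, prior to drug administration, on any study visit when compared with baseline spirometry collected at screening".
- **5.5.2 (stopping rule within the monitoring plan):** the same text as 2.6.

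Section 2.6 treats drug intolerance as a separate scenario, a "dose-dependent intolerance that will be seen at the dose escalation visit 2, or after receiving the first dose of drug on visit 1". Its FEV1 criterion is a fall above 15% "between measurements on an individual study visit".

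Section 2.2.1 describes Day 14 thus: "This is a safety and tolerability visit and will take approximately 1 hour. Subjects will complete the CFQ-R and spirometry". For Day 28 it says: "This visit will take approximately 1.5 hours. Subjects will complete the CFQ-R and spirometry". Section 2.10 plans no clinic dose at either visit and has subjects dose themselves twice daily at home after the observed doses.

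**The concern.** Section 2.13.1 gives the purpose of the primary endpoint as detecting bronchoconstriction caused by the drug. Yet the removal rule in that same section leaves out the conditions that separate a drug effect from disease. A subject who nebulizes at home and then has an acute fall at the Day 14 spirometry meets the 2.13.1 definition of an exacerbation and is removed under that label.

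Under 2.6 the same reading should not qualify, but staff need to know whether and when a dose was taken that morning. Nothing in the available text asks for this.

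What is at stake is attribution in a single-arm, open-label safety study: a tolerability signal could be recorded as cystic fibrosis disease. The label can also change management, because 2.6 returns a subject with intolerance at 90 mg to 45 mg but removes a subject with an exacerbation.

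**Working it through.** This is mainly a comparison of texts, with a few counts.

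**1. Conditions on the rule**

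| Condition | 2.6 and 5.5.2 | 2.13.1 |
|---|---|---|
| FEV1 fall above 15% | yes | yes |
| First spirometry set of a visit | yes | yes |
| Persistent | yes | absent |
| Not linked in time to nitrite | yes | absent |
| Before that day's dose | yes | absent |

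**2. Where the missing conditions matter**

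- Day 0: the first set precedes any study drug.
- Day 7: stability is checked first, with FEV1 assessed "on presentation to the Day 7 visit, an electronic nebulizer will be used to deliver 90 mg of nebulized sodium nitrite". A home dose of 45 mg that morning is possible, but at 45 mg removal follows under either label.
- Day 14: treatment is under way, the subject has drug at home, and there is one spirometry set and no clinic dose.
- Day 28: depends on step 3.
- Day 42: treatment has ended.

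**3. Is Day 28 a dosing day?**

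- Section 2.2.1 gives three weeks at 90 mg, dosed twice daily: 21 × 2 = 42 doses. If the first is the observed Day 7 dose, dose 42 falls on the evening of Day 7 + 20 = Day 27.
- Section 2.4 sets follow-up at 14 days after treatment: 42 − 14 = 28. This places the end of treatment at the Day 28 visit without saying whether a dose is taken that morning.
- The supply handed out on Day 14 lasts 15 days for a 14-day interval. The extra day could cover a Day 28 morning dose or only the ±1 day visit window.

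The protocol does not settle the question.

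**4. Is the morning dose held or timed?** The visit descriptions (2.2.1), procedures (2.10, 2.12.2) and schedule (2.11) contain no such instruction. Accountability (2.9) covers amounts, not times. The methemoglobin footnote in 2.11 mentions pre-dose and post-dose readings, but it does not govern spirometry or home dosing.

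**5. Count**

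- Treatment-phase spirometry sets: Day 0 = 3, Day 7 = 3, Day 14 = 1, Day 28 = 1; total 8.
- Affected for certain: 1 of 8 sets and 1 of 4 visits. With Day 28: 2 of 8 and 2 of 4.
- Post-dose against pre-dose comparisons within a visit: 2, 2, 0, 0. One set cannot meet the within-visit criterion of 2.6, so that criterion cannot identify intolerance at Day 14.

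The readings most at risk follow a dose by about 30 to 120 minutes, which is the plan's own acute window on Days 0 and 7. The documents give no rate of such falls, so the number of subjects cannot be derived.

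**The case against.** **The operative rule is in 2.6.** It is repeated in 5.5.2, applies to any study visit, and 2.13.1 can be read as a shorter restatement. This has weight: staff who follow 2.6 would not call a known post-dose fall an exacerbation. But 2.13.1 reads as complete in itself, and 2.6 can be applied only if the dose time is known.

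**A drug-attribution route exists at Day 14.** This stands. Table 1 grades FEV1 falls above 15% and above 25%, and bronchospasm, as toxicity. It requires no paired measurement within a visit and is not limited to visits 1 and 2. Section 2.5 has subjects followed for acute or delayed effects. Under 5.5.6.3 a test finding that ends participation becomes an adverse event, and 5.5.6.4 classes an event of uncertain, questionable relationship as drug-associated. A reader might infer that a drug-related fall at Day 14 can only be called an exacerbation; these provisions show otherwise. None of them supplies the dose time that the causality judgement needs.

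**Subjects at home on 90 mg already tolerated an observed 90 mg dose on Day 7.** This also stands. What remains is a fall that first appears with a later dose.

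**The instruction may exist elsewhere.** Consent pages, the appendix and the worksheets are not in the available text, so the gap is claimed only for what can be read.

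**Conclusion.** The point holds as a minor inconsistency with a practical gap. Section 2.13.1 omits three conditions of the stopping rule. At Day 14 the pre-dose condition cannot be verified from anything the visible protocol collects. The cost is possible misattribution of a drug effect to disease; stopping the drug is itself the safe direction.

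The size is 1 of 8 treatment-phase spirometry sets for certain, and 2 of 8 only on the assumption that a dose is taken on the morning of Day 28.

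Two stronger readings are tempting but not supported:

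- **That both later visits are affected.** The dose count, follow-up interval and supply leave Day 28 open.
- **That the sample-size test or the primary comparison is compromised.** The documents give no rate from which an effect on the 2.15.1 test could be computed. The Day 0 and Day 7 comparisons have their own pre-dose and post-dose sets. No effect on either is claimed.

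**What to change.** 1. Replace the exacerbation sentence in 2.13.1 with the full 2.6 rule: persistent, not linked in time to nitrite, and seen before drug administration. Adding the pre-dose phrase alone would leave out the first two conditions.
2. Record the time of the last study-drug dose at each spirometry.
3. If a same-day dose preceded a fall above 15%, do not classify it automatically as an exacerbation. Repeat spirometry before any sputum induction, since 2.10 notes that induction can itself narrow the airways for a time. Then assess the event under Table 1 and the 5.5.6.4 causality review.

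The cost is one sentence, one recorded time per visit and an occasional repeat spirometry.

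Holding the Day 14 morning dose until after spirometry is optional. It would make the 2.6 rule directly applicable, but it gives up any chance observation of post-dose FEV1 after Day 7, and it would still not separate a cumulative drug effect from a true exacerbation. Items 1 to 3 are worth making whichever way the sponsor decides.

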2.14 SUBJECT WITHDRAWAL

A subject may voluntarily discontinue participation in this study at any time. The investigator may also, at his or her discretion, discontinue a subject from this study at any time. Every effort should be made by the investigator to keep the subject in the study. Subjects may be withdrawn from the study prior to completion if any of the following criteria are observed:

- Intercurrent illness or an unexpected fatal or life-threatening adverse event, which requires discontinuation of study treatment
- Subject requires the use of new inhaled antibiotics between day -2 and study visit 4.
- Pregnancy
- Subject reached protocol-defined stopping criteria
- Request by the subject to withdraw from the study
- Protocol violations
- Persistent non-compliance
- Lost to follow-up
- Investigator discretion
- Study closed/terminated

2.14.1. Dropouts and withdrawals

To be considered complete, a subject must complete all study visits as specified in the protocol without violations of the protocol so significant as to obscure the response to study treatment.

Subjects who fail to complete all study required visits will not be considered complete and may not enroll at a later date and will not be replaced. A record will be kept of all subjects who fail to complete all study visits and their primary reasons for discontinuation.

In the event of subject withdrawal, subjects will be encouraged to continue all follow-up visits for safety monitoring or to continue follow up as directed by their personal primary physicians, unless the subject withdraws consent at any time (without having to justify the decision). All available data from subjects who discontinued during the study, for whatever reason, will be included in the safety analysis.

2.14.2 WITHDRAWL CRITERIA

Study treatment will be discontinued in individual subjects during the day 0 inhalation if any of the following occurs regardless of symptoms:

- **Decrease in FEV₁ by >15%** between measurements on an individual study visit.
- A decrease in systolic BP > 40 mm Hg drop from pre-dose baseline or to <80mmHg and symptomatic;
- SaO₂ drop below 88% and symptomatic or SaO₂ desaturation > 5% from baseline and symptomatic
- A single occurrence of venous methemoglobin level >5%;
- Any serious adverse event thought to be possibly related to the study treatment

Any serious adverse event thought to be possibly related to the study treatment

If a study subject tolerates the 45 mg dose but develops hypotension, sustained > 15% decrease in FEV₁ (as measured at time points (30min and 120 min), or oxygen desaturation with the 90 mg dose on day 7, the subject will be observed. If after 4 hours of observation the subject's FEV₁ returns to baseline, the subject's SaO₂ is not greater than 5% drop from baseline, and the subject's systolic BP is not greater than 40 mm Hg drop from pre-dose baseline, the subject will be re-challenged with the 45mg dose; if the lower dose is tolerated, the subject will remain in the study at the lower dose.

Subjects will be withdrawn if at any time the investigator feels that it is not in the subject's best interest to continue.

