Exclusion Criteria:	
1. Inability to provide consent2. Use of supplemental oxygen or non-invasive ventilatory support3. FEV₁ < 40%4. Awaiting lung transplantation5. Pregnancy or unwilling to comply with birth control during the intervention period6. History of glucose-6-phosphate dehydrogenase (G6PD) deficiency or any contraindication to receiving methylene blue7. Hospitalization within the past 4 weeks prior to enrollment8. Subject requires additional antibiotics or steroids within the past 4 weeks prior to enrollment9. Change in maintenance CF therapies in the past 4 weeks prior to enrollment10. Baseline systemic hypotension (systolic BP < 90 mm Hg)11. History of orthostatic hypotension or syncope12. Chronic kidney disease (creatinine > 2.5 or requiring dialysis)13. Severe anemia (Hgb <9 gm/dL in the last six months)14. History of portal hypertension or chronic liver disease, including hepatitis B and/or hepatitis C (with evidence of recent infection and/or active virus replication), defined as moderate to severe hepatic impairment (Child-Pugh Class B-C)15. History of abusing alcohol or illicit drugs within 28 days prior to study16. Severe pulmonary hypertension (mean PA pressure > 25)17. Use of sildenafil or other pulmonary vasodilator18. History of any organ transplantation19. Participation in another interventional trial in the previous 28 days
Study Endpoints:	
Primary endpoint:
 
The primary safety and efficacy endpoint is FEV₁. A sustained decrease in FEV₁ of >15% will be considered intolerable.
 
Secondary endpoints include exhaled NO (FE_{NO}), sputum nitrite concentration, quantitative bacterial cultures, percutaneous methemoglobin levels, blood pressure, and subject symptoms as measured by the CF Questionnaire-R.

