2.3 STUDY TREATMENT

The study treatment will be delivery of nebulized sodium nitrite by nebulization at the dose of 45 or 90 mg.

Table 1 Dose Limiting Toxicity Criteria

Sign or Symptom	Moderate	Severe ¹
Bronchospasm/ wheezing	Symptomatic but not requiring therapy	Symptomatic and requiring therapy
Decrease in FEV_1	>15%	>25%
SBP ²	Systolic \geq 20 mm Hg drop from pre-dose baseline AND symptomatic, or SBP <80 mm Hg AND symptomatic	Systolic > 30 mm Hg drop from pre- dose baseline AND symptomatic or requiring fluid replacement or other therapy
Dyspnea	Causes more discomfort (than a mild, easily tolerated AE) and interrupts the subject's usual daily activities	Incapacitating and causes considerable interference with the subject's usual daily activities
Cough	Causes more discomfort (than a mild, easily tolerated AE) and interrupts the subject's usual daily activities	Incapacitating and causes considerable interference with the subject's usual daily activities
Hypoxia ³	$SaO_2 > 5\%$ drop from baseline AND symptomatic	$SaO_2 \geq 10\%$ drop from baseline or $SaO_2 < 88\%$ AND symptomatic

Percutaneous methemoglobin ^{4,5}	>5% and <7%	≥7%
Other drug-related signs or symptoms ⁶	Causes more discomfort (than a mild, easily tolerated AE) and interrupts the subject's usual daily activities OR CTCAE v.4 ⁶ Grade 2 toxicity	Incapacitating and causes considerable interference with the subject's usual daily activities OR CTCAE v.4 ⁶ Grade 3 or 4 toxicity

AE = adverse event; CTCAE = Common Toxicity Criteria for Adverse Events; DLT = dose limiting toxicity; SBP = systolic blood pressure; SaO₂ = oxygen saturation (hemoglobin)

1. Severe DLT seen in any subject which is deemed to be study drug-related will preclude further dosing with nebulized sodium nitrite for that subject.
2. Moderate or Severe SBP without symptoms will be continuously monitored with BP measurements every 5 minutes. Symptomatic refers to dizziness or fainting. Discontinuation of further dosing or dose escalation will be based upon follow up blood pressure measurements, subject symptoms and physician-investigator discretion (see Stopping Rules).
3. Moderate or Severe SaO₂ without symptoms will be continuously monitored and recorded every 5 minutes until return of saturation > 92%.

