2.5 SAFETY MONITORING

Prior studies suggested that hypotension and methemoglobinemia may occur with the use of sodium nitrite. The study treatment of inhaled nitrite will be used safely with careful monitoring and prompt discontinuation of the study treatment in response to systemic hypotension with definitions of dose limiting toxicity. The presence of severe DLT deemed to be study-drug related will lead to a discontinuation of the study treatment.

Following study drug treatment, subjects will be evaluated as an outpatient at the clinic on Day 42 (+/- 5 day window). Interval study visits (days 7, 14 and 28) have been included in the study design to ensure subject safety. Subjects will be followed for evidence of acute or delayed adverse effects from the study treatment and to assess their clinical status. All adverse events experienced by subjects will be collected from beginning of visit 1 through final study visit. Study subjects will be routinely questioned about adverse events at study visits. The study investigators will evaluate all subject reported and observed AEs. All untoward medical occurrences observed in subjects receiving the study drug will be recorded on the participants' adverse event worksheets by the study coordinator under the supervision of the principal investigator. AEs occurring pre-treatment, during active treatment and post-treatment will be summarized separately. Subjects continuing to experience toxicity at the off study visit may be

contacted for additional assessments until the toxicity has resolved or is deemed irreversible. If possible, symptoms should be managed symptomatically. In the case of toxicity, appropriate medical treatment should be used.

In addition to these formal evaluations, subjects will be encouraged to immediately contact the study investigator and/or the study coordinator with questions, concerns, or to report new symptoms that occur during their study participation. If appropriate, based upon the evaluation, medical treatments will be provided to subjects, including appropriate referral to physicians or other services at the UPMC.

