***Stopping Rule:**

Two distinct scenarios in which subjects must be removed from the study are anticipated.

First, the subject experiences a CF respiratory exacerbation marked by a persistent drop in FEV₁ >15% that is not temporally associated with nebulized sodium nitrite administration. The drop in FEV₁ would be seen on the first set of spirometry at a visit, prior to dosing of nebulized sodium nitrite for that day. In this case, subjects will be removed from the study and referred to their pulmonologist for treatment of the CF respiratory exacerbation.

- Drop in FEV₁ >15% on the first set of spirometry, prior to drug administration, on any study visit when compared with baseline spirometry collected at screening.

In the second scenario, nebulized sodium nitrite is associated with a dose-dependent intolerance that will be seen at the dose escalation visit 2, or after receiving the first dose of drug on visit 1. Specific intolerances of concern are acute bronchospasm, hypotension or methemoglobinemia. In this case, if any one of the below occurs at the 45 mg dose, subject will be removed from the study; if any occur at the 90 mg dose, the subject will return to the previously tolerated dose of 45 mg.

- Decrease in FEV₁ by >15% between measurements on an individual study visit.
- A decrease in systolic BP > 40 mmHg drop from pre-dose baseline or to <80mmHg and symptomatic
- SaO₂ drop below 88% and symptomatic or SaO₂ desaturation > 5% from baseline and symptomatic
- A single occurrence of venous methemoglobin level >5%
- Any serious adverse event thought to be possibly related to the study treatment

The Investigator will prepare a detailed written summary of serious, unexpected, and treatment related adverse events, and will compare, and contrast the event with prior events. The detailed written summary will be provided to the DSMB and the IRB.

In addition, the DSMB Report addressed the following information will be submitted to the IRB at the time of continuing review annually or more often as required:

- A list of the research personnel who participated in the data and safety monitoring.
- The frequency of monitoring that took place during the renewal intervals and/or the dates that data and safety monitoring was conducted.
- A summary of cumulative data related to unanticipated problems (including adverse events) including a determination of causality and whether the risk to benefit assessment has changed.

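### At 90 mg the FEV₁ dosing rules conflict: a drug-related fall above 25% both ends dosing and leads to 45 mg, and a transient fall above 15% requires step-down in some sections but not in others

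*Combined protocol and SAP*

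**What the plan says.** **Severe falls.** Table 1 (section 2.3) grades an FEV₁ decrease above 15% as moderate and above 25% as severe. Note 1 reads: "Severe DLT seen in any subject which is deemed to be study drug-related will preclude further dosing". Section 2.5 says the same: "The presence of severe DLT deemed to be study-drug related will lead to a discontinuation of the study treatment".

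**Step-down at 90 mg, any fall.** Sections 2.6 and 5.5.2 list the trigger as "Decrease in FEV1 by >15% between measurements on an individual study visit", and the action is: "if any occur at the 90 mg dose, the subject will return to the previously tolerated dose of 45 mg". Neither section requires the fall to be sustained, sets an upper limit, or attaches a recovery condition.

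**Step-down at 90 mg, sustained fall.** Section 2.13.1 covers a subject who "has a sustained decrease in FEV₁ after getting the first 90 mg dose, the subject will remain on the 45 mg dose" for the rest of the study. Section 2.14.2 acts at 90 mg on a "sustained > 15% decrease in FEV₁ (as measured at time points (30min and 120 min". It then allows a 45 mg re-challenge if FEV₁, oxygen saturation and blood pressure have recovered after 4 hours of observation.

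**Visit 2 procedure.** Under 2.2.1, a subject who did not tolerate 90 mg and has recovered within 4 hours proceeds as follows: "the subject will be re-challenged at this visit with a 45 mg dose". That section does not define tolerance.

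**At 45 mg.** Sections 2.6, 5.5.2 and the day 0 list in 2.14.2 all stop the subject for any fall above 15% within the visit. The synopsis instead says: "A sustained decrease in FEV₁ of >15% will be considered intolerable". Section 2.13.1 also uses the sustained wording at 45 mg.

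**The concern.** Bronchoconstriction is the hazard that the primary endpoint is there to detect, and day 7 is the first exposure to the target dose. Staff at that visit need one instruction for each spirometry result. As written, a subject with a drug-related fall above 25% is barred from further drug by two provisions and sent to 45 mg, or considered for it, by five others. A subject with a brief fall above 15% steps down or does not, depending on which section is open. The first conflict concerns the subject's safety. The second concerns whether subjects are handled alike.

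**Working it through.** The point rests on the rules themselves, so the check is to apply each one to two day 7 results after 90 mg.

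- **Result A:** a fall above 25%, judged drug-related, present at 30 and 120 minutes, with FEV₁, saturation and blood pressure recovered by 4 hours.
- **Result B:** 18% below pre-dose at 30 minutes and 5% below at 120 minutes (18 > 15, 5 < 15).

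| Section | Result A | Result B |
|---|---|---|
| Table 1 note 1 | No further dosing | Moderate grade; note 1 does not apply |
| 2.5 | Treatment ends | Severe-toxicity rule does not apply |
| 2.6 | 45 mg | 45 mg |
| 5.5.2 | 45 mg | 45 mg |
| 2.13.1 | 45 mg | No FEV₁ trigger |
| 2.14.2 | Re-challenge at 45 mg; continue if tolerated | No FEV₁ trigger |
| 2.2.1, visit 2 | Re-challenge at 45 mg | Depends on what tolerated means |

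**Result A.** The first two rows forbid what the other five direct or allow. If the fall above 25% were not sustained, 2.13.1 and 2.14.2 would drop out, but 2.6 and 5.5.2 would still direct 45 mg. None of the five contains an exception for a severe toxicity.

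**Result B.** The unqualified 15% list in 2.14.2 does not close the gap, because it is confined to the day 0 inhalation. Section 2.2.1 does not close it either. A coordinator who takes the synopsis definition of intolerable would count this subject as having tolerated 90 mg, and 2.2.1 then dispenses 8 days of drug at that dose.

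**Precedence.** No section says which rule governs. The step-down and re-challenge texts do not refer to Table 1 for a severe fall.

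**Consequence for one subject.** Treatment runs from day 7 to day 28, which is 28 − 7 = 21 days. At two doses a day that is 21 × 2 = 42 doses, nearly all taken at home. Under Result A the choice is between none of these and about 42 doses of 45 mg. Under Result B it is between 45 mg and 90 mg twice daily, that is 90 or 180 mg a day.

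**The case against.** **Table 1 governs.** Note 1 is categorical and 2.5 repeats it. The 15% step-down threshold is Table 1's moderate grade, so the natural combined reading is that moderate means step down and drug-related severe means stop. That is sensible and probably what was intended, but the protocol does not say so, and 2.6 and 5.5.2 state their action without exception.

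**There are safeguards.** Re-challenge under 2.2.1 and 2.14.2 needs recovery within 4 hours and repeats the observation, and the investigator may withdraw a subject at any time. This stands, and it limits the harm. A reader might infer that every subject with a fall above 25% would be given more drug. The documents do not support that: 2.13.1 and 2.14.2 require a sustained fall, re-challenge requires recovery, and the Table 1 bar itself depends on the fall being judged drug-related. Discretion to withdraw still does not reconcile two mandatory instructions.

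**The transient case is a gap, not a contradiction.** Sections 2.13.1 and 2.14.2 do not say that such a subject stays on 90 mg, so staff who follow 2.6 breach nothing. The parenthesis in 2.14.2 may also merely name the spirometry times rather than define sustained. Both points are fair. But a fall of 18% that becomes 5% is not sustained on any ordinary reading, so the sections still lead to different actions.

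**The sample size or analysis is affected.** A reader might infer this, because 2.15.1 speaks of discontinuation and a step-down is not one. The documents do not support it. Section 2.15.1 gives the binomial test only as justification for the sample size, and its 82% power at n = 33 reproduces (5 or more events: exact power 0.818, alpha 0.045). The primary endpoint in 2.13.1 compares FEV₁ before and after the 90 mg dose. Section 5.5.6.3 makes a test finding that changes dosing an adverse event, and 2.15.2 tabulates adverse events. Intolerance of 90 mg would therefore be recorded.

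**Conclusion.** The rules are wrong as written and should be fixed. Both conflicts are in the current text and both apply at the same visit. The severe-fall conflict matters more, because following 2.6 or 5.5.2 literally gives drug to a subject whom Table 1 and 2.5 exclude. The transient-fall conflict leads to inconsistent dosing. The number of subjects affected cannot be estimated: the documents give neither the expected share with a fall above 25% nor the share of falls that recover by 120 minutes. The ceiling is the 35 planned subjects, less any who do not reach the 90 mg dose. The conclusion assumes that each section is meant to be followed as it stands. If the sponsor always intended Table 1 to prevail, the first part becomes a missing cross-reference, but the text still needs it.

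**What to change.** 1. In 2.2.1 (visit 2), 2.6, 2.13.1, 2.14.2 and 5.5.2, state that a drug-related FEV₁ fall above 25% at 90 mg ends dosing, with no return to or re-challenge at 45 mg, in line with Table 1 note 1 and 2.5.
2. Use one 90 mg FEV₁ trigger in all five sections, measured against the same visit's pre-dose value, and define tolerance in 2.2.1 by reference to it. The rule already in 2.6 and 5.5.2, any fall above 15%, is the safer default.
3. At 45 mg, align the synopsis and 2.13.1 with the any-fall rule in 2.6, 2.14.2 and 5.5.2.

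The cost is a wording amendment. The pre-dose, 30-minute and 120-minute spirometry is already scheduled. The downside is that, under the any-fall rule, some subjects with only a transient fall will step down to 45 mg.
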